3.2 Phase 2 Design

Once the ipilimumab dose is established for each study arm, the randomization between the immediate and delayed arms will resume accruing a total of 27 evaluable randomized patients per study arm.

Randomized patients treated in the phase I at the same dose used in the Phase 2 study will be included for immune response analysis; thus patients accrued in the randomized component of the Phase I trial can be included for analysis of the study objectives.

Once written informed consent is obtained and the patient has undergone screening and determined to be eligible for the trial, treatment with SipT will begin. The patient will be randomly assigned following the second dose of SipT to one of the two treatment groups in a 1:1 ratio using a block design to maintain a balance in treatment assignment. Randomization will be stratified by site (UCSF and MD Anderson). The randomization will be performed by the study statistician at UCSF. At the time of randomization, a unique patient study identification number will be assigned to each patient. This study identification number must be included on all submitted forms and specimens.

Patients will receive induction treatment with 4 doses of ipilimumab on a 21-day cycle. As durable disease stabilization and/or objective tumor response can be seen after early progression, it is recommended that, in the absence of dose-limiting toxicities, all four doses of ipilimumab be administered over the initial 12 weeks even in the setting of apparent clinical progression, providing the subject's performance status remains stable.

All subjects who enter the induction period, including those who may have discontinued treatment for drug-related AEs and/or who have evidence of clinical progression during the induction period, should obtain a 12-week tumor assessment.

Clinical progression warranting alternative anti-cancer treatment should be considered only in subjects whose overall tumor burden appears to be substantially increased and/or in subjects whose performance status is decreased.

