Secondary Immune Objectives: The sample size with 27 patients in each arm is sufficient to detect a mean difference between the two study arms in immune modulation, a secondary objective, for an effect size (standardized unit) of at least 0.69 for normally distributed variables. Similarly, the sample size is sufficient to detect at least a 37% difference between the two treatment groups in proportions of patients displaying a specific outcome using Fisher's exact test (e.g. 33% versus 70% achieving a certain change in an immune parameter). For both types of tests a level of significance of 0.05 for a directional test and power of at least 0.80 is assumed. Directional tests will be performed to test for an effect due to the timing of ipilimumab. A directional test is being used because a greater immune effect is expected with immediate administration of ipilimumab.

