9.3 Methods for Analysis

9.3.1 Primary Endpoints

9.3.1.1 *Safety Lead-in: Assess the safety of combining ipilimumab with SipT.*

Toxicities will be reported for each study arm at each dose of ipilimumab administered with descriptive statistics (e.g. proportions) by tabulating the frequency of the maximum grade occurring for each patient for each type using NCI CTC v. 4.0 criteria. As described above the type and grade of all such IraEs will be tabulated by treatment arm. Toxicity results will be presented indicating occurrences during the first 20 weeks of protocol therapy and those occurring later.

9.3.1.2 *Phase 2: Determine whether the timing of ipilimumab administration impacts PAP and PA2024 specific immune responses by SipT*

The primary immune study hypothesis to assess the frequency of observing an immune response to PAP and/or PA2024 by week 20, when the induction ipilimumab therapy is completed, for each of the two ipilimumab schedules will be tested using the single sample binomial exact test. The IgM and IgG antibody responses to PAP and PA2024 will be assessed with an ELISA assay at baseline and week 20 after the start of sipT treatment (day 113 of study treatment). A positive response will be defined as a titer > 1:400. The primary hypothesis will be tested by comparing the proportion of patients achieving an IgG immune response to PAP or PA2024 to the null hypothesis of 15% (based off an observed anti-PAP IgG response rate of 17.7% seen at a similar time interval in patients treated with sipuleucel-T in the three phase 3 clinical trials⁴⁶. using a single sample exact test for binary variables as defined above in the sample size justification. The same single sample test will be performed for IgM antibodies. The positive immune proportion for both IgG and IgM antibodies to PAP and to PA2024 with 95% confidence intervals will be used to summarize the results for each study arm. No adjustment for multiple comparisons will be made.

Exploratory analyses investigating the change in antibody response from baseline to week 20 when response is considered as a binary variable (positive or negative) will be investigated using the Mantel-Haenszel chi square statistic stratified by treatment arm. When the ELISA results are treated as continuous variables the change in each immune response will be analyzed using analysis of variance (ANOVA) methods.

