9.3.2.3 Modulation of Effector and Regulatory T Cells

The secondary outcome measures of T cell immune activation will be compared between the two treatment arms. Exploratory analyses of antigen-specific T cell responses to PAP and PA2024 will be measured at weeks 0, 4(study day 1), 7(day 22), 10(day 43), 13 (day 64), 16 (day 85), 20 (day 113), 32 (day 197) with IFNg ELISPOT. Samples will be obtained just prior to treatment. A T cell response to each of the antigens will be defined as ≥ 10 spots/300,000. For each antigen (PAP and PA2024), the proportion of positive responses by treatment arm at week 20 will be calculated and presented with 95% confidence intervals. Agreement in antibody and T cell responses will be explored at each time point with McNemar's test for paired binary data. In addition, a test of when a T cell immune response is first recognized will also be identified using ANOVA methods when the T cell response is evaluated as a continuous variable. There will not be any adjustment for multiple comparisons for these exploratory analyses.

Exploratory ANOVA analyses for mixed models will also be used to compare the magnitude or the change from baseline in activated CD4 and CD8 T cells to week 7, 10, 13, 16, and 20 of treatment between the two treatment arms. Activation markers to be assessed on CD4 and CD8 T cells by flow cytometry will include ICOS/ICOS-L; OX40/OX40-L; 41BB/41BB-L; PD-1/PD-L1 and PD-L2; CD69, and HLA-DR. Similar comparisons of the magnitude or change from baseline in FoxP3+ CD4+ Regulatory T cells at these same time points will be evaluated.

Additional exploratory analyses again using ANOVA methods will be performed to determine whether there is a difference in baseline levels or change by week 14 and 20 in T cell activation markers between those achieving a PSA decline of at least 30% or not.

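### The between-arm T cell comparisons name no baseline adjustment and leave open whether the value or the change is analysed, which gives up precision on a secondary objective.

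*Combined protocol and SAP*

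**What the plan says.** Section 2.2 lists, as a secondary objective, whether the timing of ipilimumab alters the modulation of effector and regulatory T cells. Section 9.3.2.3 gives the analysis: exploratory mixed-model ANOVA "will also be used to compare the magnitude or the change from baseline in activated CD4 and CD8 T cells" at weeks 7, 10, 13, 16 and 20 between the two arms, with similar comparisons for FoxP3+ CD4+ regulatory cells. The secondary endpoint text in the synopsis is narrower. For these same cells it names only the change from baseline, through week 20.

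The sizing for the secondary immune objectives is in section 9.1.2: "The sample size with 27 patients in each arm is sufficient to detect a mean difference between the two study arms" in immune modulation, "for an effect size (standardized unit) of at least 0.69 for normally distributed variables". It adds: "For both types of tests a level of significance of 0.05 for a directional test and power of at least 0.80 is assumed".

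No section names baseline as a covariate in these models. Section 9.3.2.1 plans tests of whether baseline immune parameters are comparable between the arms, which does not adjust for them.

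**The concern.** The raw follow-up value ignores baseline. The change score subtracts baseline in full, which adds noise when baseline and follow-up are weakly correlated. Using baseline as a covariate lets the data set the weight, so it does at least as well as either option. With 27 patients per arm the difference can be material, and the arms may differ at baseline by chance.

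The wording also allows two outcomes for each marker and visit without saying which one decides. Many activation markers, five visits and no multiplicity adjustment in that section make the open choice harder to defend when results are reported.

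**Working it through.** **Inputs from the documents.** 27 per arm, 0.69 standardized units, one-sided 0.05 and power of at least 0.80 (section 9.1.2); allocation "in a 1:1 ratio using a block design to maintain a balance in treatment assignment" (section 3.2).

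**Assumptions, because the documents are silent.** Rho from 0.2 to 0.7; equal SD at baseline and follow-up, set to 1; the 0.69 is in SDs of the raw value.

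**1. Reproduce the plan's figure.** For an unadjusted two-group comparison the noncentrality is 0.69 × √(27/2) = 2.535 on 52 degrees of freedom. Power is 0.804, and the detectable difference at 80% power is 0.686 SD. The two-sided figure would be 0.777. The stated 0.69 is therefore reproduced as a one-sided, unadjusted two-group figure.

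**2. Variance of each analysis at one visit.**
- Raw value: 1
- Change: 2(1 − rho)
- Baseline-adjusted: 1 − rho²

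Adjusted over raw is 1 − rho². Adjusted over change is (1 − rho²)/[2(1 − rho)] = (1 + rho)/2. Both ratios are below 1 for any rho strictly between 0 and 1. At rho 0.5 both equal 0.75.

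**3. Power for 0.69 raw-value SD, and detectable difference at 80% power, at one visit** (noncentral t; 52 degrees of freedom, 51 when adjusted).

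| rho | SD, change | SD, adjusted | Power: raw / change / adjusted | Detectable SD: raw / change / adjusted |
|---|---|---|---|---|
| 0.2 | 1.265 | 0.980 | 80 / 63 / 82% | 0.69 / 0.87 / 0.67 |
| 0.3 | 1.183 | 0.954 | 80 / 68 / 84% | 0.69 / 0.81 / 0.65 |
| 0.5 | 1.000 | 0.866 | 80 / 80 / 89% | 0.69 / 0.69 / 0.59 |
| 0.7 | 0.775 | 0.714 | 80 / 94 / 97% | 0.69 / 0.53 / 0.49 |

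**4. If the contrast is averaged over the five visits.** Assume the same rho between all visits and a constant difference of 0.69 SD. The mean of five values has variance (1 + 4rho)/5. The change version has (1 + 4rho)/5 + 1 − 2rho, and the adjusted version has (1 + 4rho)/5 − rho².
- Rho 0.2: raw 0.36, change 0.96, adjusted 0.32. Power with the change score is 82%.
- Rho 0.3: raw 0.44, change 0.84, adjusted 0.35. Power with the change score is 86%.

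The change score now passes 80%, but adjustment still has the smallest variance.

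**5. The open choice of outcome.** With no true effect, the raw-value and change statistics have correlation √((1 − rho)/2), which is 0.59 at rho 0.3 and 0.39 at rho 0.7. Taking whichever one-sided 5% test is significant gives a simulated false-positive rate of roughly 8% to 9% per marker and visit over that range. This is what the missing rule would allow. The plan does not say that anyone will choose this way.

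**The case against.** Much of the case on the other side stands.

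- **The planned sensitivity.** A reader might infer that the plan misses its own 0.69 SD. The documents do not support this. The raw-value analysis meets 0.69 by construction. The change score falls short only if rho is below 0.5, the 0.69 is on the raw-value scale, and contrasts are made visit by visit. Section 9.1.2 does not say which SD its standardized unit refers to; if it is the SD of the change, the change analysis meets 0.69. Section 9.3.2.3 does not say whether visits are pooled.
- **Silence is not exclusion.** Mixed-model ANOVA can carry a baseline term. The model is under-specified, and adjustment is not ruled out.
- **The outcome is not wholly undefined.** The synopsis names the change from baseline for these cells. Section 9.3.2.3 is looser than the endpoint it serves.
- **No bias.** Under randomization both listed analyses are unbiased, and chance baseline imbalance is part of their sampling error.
- **The antibody analysis.** Section 9.3.1.2 says: "When the ELISA results are treated as continuous variables the change in each immune response will be analyzed using analysis of variance (ANOVA) methods". One might read the same weakness there, but that sentence states no between-arm comparison. The point applies to it only if the arms are in fact compared.
- **Weight.** The models are labelled exploratory, the trial is described as non-comparative, and the primary single-sample binomial test does not depend on them.

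None of this restores the lost precision or supplies a rule for choosing the outcome.

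**Conclusion.** The point holds as a recommendation on efficiency and specification. For any rho strictly between 0 and 1, baseline adjustment beats both planned options. At one visit and rho 0.5 it cuts the variance by 25% against either, and power for 0.69 raw-value SD rises from 80% to 89%. At rho 0.2 the gain over the raw value is small (80% to 82%). At rho 0.7 the gain over the change score is small (94% to 97%). Since rho is unknown at planning, adjustment is the one choice that does well across the range.

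The variance ratios rest on equal SDs at baseline and follow-up. The power figures rest also on a single-visit contrast and on reading 0.69 in raw-value SDs. The need to name one outcome does not depend on rho.

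**What to change.** In section 9.3.2.3, replace the choice between the value and the change with one model for each marker: a mixed model of the post-baseline values with arm, week, arm-by-week, baseline value, baseline-by-week and site (the stratification factor), estimating the arm difference at each week.

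Also:
- **Define baseline as the pre-randomization week 0 sample.** Section 9.3.2.3 schedules antigen-specific T cell samples at both week 0 and week 4 (day 1). Day 1 falls after randomization, which section 3.2 places after the second SipT dose. Section 6.2.1.1 allows the baseline immune draw at any time after consent, so the definition has to be written down.
- **Align the synopsis endpoint.** Note there that, with baseline as a covariate, the arm effect is the same whether the value or the change is modelled.
- **State the SD scale of the 0.69 in section 9.1.2.**
- **If arms are compared on continuous ELISA results (section 9.3.1.2), adjust in the same way.**

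The cost is a few sentences and a few degrees of freedom: one per baseline term, up to five with baseline-by-week. No new data are needed.

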9 STATISTICAL METHODOLOGY

9.1 Sample Size Considerations

9.1.1 Safety Lead-in

Six patients at the 3 mg/kg dose of ipilimumab will be randomized to Arm 1 and 2, immediate versus delayed ipilimumab after 4 doses of SipT. If DLTs are encountered as defined above (Section 3.1), then one or both arms may be discontinued. 6 patients will be required to complete this phase of the study.

9.1.2 Phase 2

Primary Immune Objective: This is a multicenter non-comparative randomized Phase 2 trial with the primary objective of immunologic efficacy in addition to safety. Immune response is defined as an IgG antibody response to either PAP or PA2024 by study week 20. The IgG antibody response will be determined with an ELISA assay with a positive response defined as titer > 1:400. To achieve a 40% immune response rate indicating immune activity versus a null hypothesis of 15% indicating lack of immune activity assuming a 2-sided type I error of 5% and 81% power will require 27 total patients per arm. This is based upon the exact binomial test for a single sample. The null hypothesis of 15% is based off an observed anti-PAP IgG response rate of 17.7% seen at a similar time interval in patients treated with sipuleucel-T in the three phase 3 clinical trials⁴⁶. Therefore, an additional 21 patients beyond the safety lead-in phase will be accrued to each arm (an additional 42 patients). The total number of evaluable patients for the Phase 2 study will be 54 patients with accrual up to 66 patients possible. Patients will be accrued at UCSF and MDACC with the randomization to ipilimumab timing stratified by institution.

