9.2 Stopping Rules

9.2.1 Stopping Rules for Efficacy

There will be no interim analysis for efficacy due to the small sample size of each treatment arm. Although a secondary outcome measure is PSA decline, additional exploratory analyses will be performed to investigate the relationship between evidence of immune activation and clinical response to aid in designing future investigations.

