9.3.2 Secondary Endpoints

9.3.2.1 PSA Decline

Descriptive statistics will be used to characterize the disease and treatment factors for patients accrued to each study arm. The two treatment arms will be compared for comparability of baseline disease features and immune parameters using a chi square test for categorical variables, a t test for normally distributed continuous variables and the nonparametric Mann-Whitney test when the normality assumption cannot be assumed.

Descriptive statistics will be calculated to characterize the proportion of patients achieving a PSA decline of at least >30% and >50% and presented along with the 95% confidence intervals for each study arm. The maximum overall change in PSA will be summarized by waterfall plots for each study arm. Similarly, the proportion of patients achieving an objective response will also be determined. Descriptive statistics will be presented for each study arm to summarize response according to important disease features such as LDH (abnormal vs. normal) and prior treatment (radiation therapy, RP, systemic steroid usage > 3 months). Descriptive statistics will be used to summarize time to PSA progression. The Kaplan-Meier product limit will be used to estimate the probability of time to PSA progression with durations measured from the start of protocol therapy. For each study arm the median time to progression with 95% confidence intervals will be presented to summarize clinical efficacy.

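### The exploratory marker-versus-PSA analysis in 9.3.2.3 uses only a split at a 30% PSA decline; adding PSA change on its full scale would recover substantial power if the relation is roughly linear

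*Combined protocol and SAP*

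**What the plan says.** Section 9.3.2.3 closes with this plan: "Additional exploratory analyses again using ANOVA methods will be performed to determine whether there is a difference in baseline levels or change" by weeks 14 and 20 in "T cell activation markers between those achieving a PSA decline of at least 30% or not". The marker stays continuous as the outcome, and PSA is reduced to two groups. No sample size, significance level or power is attached to the comparison.

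Section 7.1.3.1 defines the 30% group as a fall of at least 30% from baseline, confirmed by a second measurement at least 4 weeks later. Section 7.1.3 has PSA measured on day 1 of every cycle, and the study calendar continues it through follow-up. Section 9.3.2.1 already derives a continuous quantity per patient: "The maximum overall change in PSA will be summarized by waterfall plots for each study arm".

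Section 9.2.1 promises, in general terms, further exploratory work to "investigate the relationship between evidence of immune activation and clinical response to aid in designing future investigations". It names no method and does not refer to the 30% comparison.

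**The concern.** A two-group split treats a 29% fall like a doubling of PSA, and a 31% fall like a 95% fall. If marker levels move gradually with PSA, the ordering within each group is information that the analysis discards. The loss grows as the responder group shrinks.

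The plan does not do this elsewhere. Section 9.3.1.2 analyses the ELISA results both as positive or negative and as continuous values, and 9.3.2.3 itself treats the ELISPOT result both ways. Only in the marker-versus-PSA comparison is PSA limited to a single cut, and no reason is given. At stake is how much can be learned about immune activation and PSA outcome from data that are being collected anyway.

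**Working it through.** **1. The plan's own figures.** None is stated for this comparison, so the neighbouring ones (9.1.2) were checked to confirm the working sample size.
- Primary: the target rate is 40% and the null rate is 15%, with the design stated as "assuming a 2-sided type I error of 5% and 81% power will require 27 total patients per arm". With the upper tail held to 0.025, at least 8 of 27 has null tail 0.0398 (too large) and at least 9 of 27 has 0.0138. Power of the latter at 40% is 0.816, which reproduces 81%.
- Secondary, between arms: "an effect size (standardized unit) of at least 0.69 for normally distributed variables". At 27 versus 27 and one-sided 0.05, power is 0.804, which reproduces at least 0.80.
- Total: "The total number of evaluable patients for the Phase 2 study will be 54 patients". So n = 54 is used below, assuming that every patient contributes.

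**2. Size of the responder group.** The documents give no 30% rate. The series with counts in 1.2.4 run from 1/20 = 5% to 5/9 = 56%, that is 0.05 × 54 ≈ 3 to 0.56 × 54 ≈ 30 patients. Pooling the chemotherapy-naive or unselected series: (2+5+5+5+4+2+1)/(14+28+9+16+15+23+20) = 24/125 = 19%, or about 10 of 54. These are mostly 50% declines, so a 30% cut should give at least as many.

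**3. Information kept by a split.** For a normally distributed PSA change cut at responder fraction q, the fraction kept is φ(z_q)² / [q(1−q)], where φ is the normal density and z_q the cut point. This gives 0.342 at q = 10%, 0.490 at 20% and 0.576 at 30%.

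**4. Power by simulation.** 30,000 runs, n = 54, two-sided 0.05, marker and PSA change bivariate normal. The correlations and responder fractions are assumptions.

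| Correlation | Pearson | Spearman | Split, 10% | Split, 19% | Split, 30% |
|---|---|---|---|---|---|
| 0.30 | 60.5% | 55.8% | 24.2% | 32.4% | 38.4% |
| 0.35 | 74.9% | 69.3% | 31.1% | 42.1% | 50.0% |
| 0.40 | 86.3% | 81.9% | 38.6% | 53.4% | 62.5% |

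- Loss against Pearson: from 60.5 − 38.4 = 22 points to 86.3 − 38.6 = 48 points.
- Loss against Spearman: from 55.8 − 38.4 = 17 points to 81.9 − 38.6 = 43 points.
- At the pooled 19% rate, against Pearson: 28 to 33 points.
- With one-sided 0.05, against Pearson: about 18 to 41 points.

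**5. Outside that range, against Pearson.**
- Correlation 0.2: about 11 to 18 points at 10% to 30% responders.
- Correlation 0.5: 97.6 − 83.0 = 15 points at 30% responders, but 97.6 − 56.7 = 41 at 10%.
- Correlation 0.6: about 4 to 6 points at 25% to 30% responders, and more with fewer responders.
- Step model (marker 0.9 SD higher only beyond the cut): the split wins. At 20% responders it has 72% power against 42% for the continuous test.

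**6. Which PSA variable.** The ratio of lowest on-study PSA to baseline looks natural, but in a patient whose PSA rises steadily the lowest value is simply the earliest one, so such patients bunch near a ratio of 1. In a simulation with 50% to 60% of patients bunched (correlation 0.30 to 0.37), the Spearman gain over the split fell to about 8 to 25 points at 10% responders and to between −8 and +3 points at 30%. These figures depend on how the bunching is modelled; exact ties erode the gain less. A fixed-visit PSA change avoids the problem.

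**The case against.** The strongest reply is that the comparison is labelled exploratory, carries no stated power and feeds no decision, so power at an assumed correlation is a weak yardstick. The cut is also not arbitrary: 30% is a listed secondary endpoint, section 7.1.3 equates response with PSA decline, and 30% gives a larger group than 50% would. Section 9.2.1 leaves methods open, so a continuous analysis is unspecified rather than excluded. All of this stands. It sets the severity and is a reason to keep the 30% comparison, but it gives no reason to have that comparison alone.

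A reader might go further and infer four things that the documents do not support:
- That the responder group will be very small. No 30% rate is given, and the cited rates imply anything from about 3 to 30 of 54.
- That the power loss is a fixed property of the plan. It depends on linearity, the correlation, the responder fraction and the sidedness, and it reverses under a step at 30%.
- That a true association would probably be missed. At a correlation of 0.37, split power is 56% to 58% with 30% to 40% responders, so detection is then more likely than not.
- That 9.2.1 relies on this comparison. It does not name it.

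**Conclusion.** The point holds in conditional form. The only specified analysis of T cell activation markers against PSA outcome discards the scale of a measurement that the trial already has. If the relation is roughly linear with a correlation of 0.3 to 0.4, 10% to 30% of 54 patients respond and the test is two-sided at 0.05, the cost is about 22 to 48 points of power against Pearson, or 17 to 43 against Spearman. It is smaller at weaker correlations, and at strong correlations with a larger responder group. It becomes a gain for the split if markers change only at the 30% cut, which nothing in the documents leads one to expect. The correlations and responder rates are assumptions, not figures from the plan. Severity is low: no primary or secondary conclusion changes.

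**What to change.** In 9.3.2.3, add as the main exploratory analysis: for each marker, relate the baseline level and the change to the log ratio of PSA at one fixed scheduled visit (for example day 85) to baseline PSA, by linear regression adjusted for arm or by rank correlation. Name the visit and its window in advance, and report how many patients lack a value. Do not use the lowest on-study PSA. Adjustment for arm is worthwhile because on the study calendar the arms are at different points of their ipilimumab course on any given study day. Keep the confirmed comparison of at least 30% against less than 30% as a secondary display; it also covers the case of a real step at that cut.

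The cost is a sentence or two of SAP text and a few lines of code, with no new data. The downsides are small: a correlation is slightly less familiar to clinicians than a responder split, some values will be missing at the chosen visit, and power is lower if the true relation is a step at 30%.
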